7. INVESTIGATIONAL PLAN

This study is a 12-month, open-label, randomized, multicenter study which will evaluate the safety and effects of CVT-301 for the treatment of up to 5 OFF episodes per day in PD patients experiencing motor fluctuations (OFF episodes) and will include a concurrent observational cohort of PD patients managed using the usual standards of care. Patients must be CVT-301-naïve, however, any patients that were enrolled from the CVT-301-002 and CVT-301-003 studies under the previous version of this protocol will be allowed to continue in the study. Patients will be randomized in a 2:1 ratio to the CVT-301 treatment group (CVT-301 at a target nominal respirable dose of 50 mg LD FPD) or the observational cohort. Randomization will be differentiated by the patient's Hoehn and Yahr stage (<2.5 versus ≥ 2.5) to balance the severity of disease across each group and by screening spirometry (FEV1 $<60\%$ of predicted *or* FEV1/FVC ratio $<70\%$ versus FEV1 $\geq 60\%$ of predicted *and* FEV1/FVC ratio $\geq 70\%$).

Patients assigned to the CVT-301 treatment group may use the prescribed dose of CVT-301 as needed for the treatment of up to 5 OFF episodes per day in addition to their standard PD medications which may be modified as needed for symptomatic treatment over the 12-month study. Each treated episode will require 2-capsule inhalations (i.e., 2 capsules used in the inhaler per treated episode) to deliver the dose.

Patients assigned to the observational cohort will not receive CVT-301 but will be permitted to be managed using their standard PD medications and other PD treatment modalities, which may be modified as needed for symptomatic treatment in accordance with usual practice over the 12-month study.

For both the CVT-301 treatment group and the observational cohort, additions to and/or modification of the patient's usual PD treatment regimen may include any PD treatments that are currently approved in the patient's region. However, oral PRN LD formulations are not permitted for CVT-301-treated subjects (refer to [Section 9.4.2](#) for a list of prohibited treatments and prohibited medications). For CVT-301-treated patients, the total daily LD dose of the modified PD treatment regimen (not including CVT-301) must not exceed 1600 mg per day.

The study includes a screening period of up to 35 days (with 2 screening visits) and a treatment period of approximately 12 months (52 ± 2 weeks) (with 6 treatment/observational visits) plus an additional follow-up at a pulmonary laboratory 4 to 5 weeks after the last treatment/observational visit. A longer screening period may be permitted with approval from the Sponsor. Planned treatment/observational visits will occur at 0 (pre-dose, baseline) and approximately 1, 3, 6, 9, and 12 months. For the CVT-301 treatment group, these visits will be treatment visits and for the observational cohort, these will be observational visits. All patients, regardless of treatment group, will be required to attend all of the screening visits and all of the treatment/observational visits. Assessments for DLco will be performed at a pulmonary laboratory outside of the clinic prior to the TV/OV1, within 2 weeks prior to the 3-, 6-, 9-, and 12-month visits, and 4 to 5 weeks after TV/OV6.

If a patient in the CVT-301 treatment group develops significant tolerability concerns that in the opinion of the investigator are of a severity that should necessitate a reduction in dose, including, but not limited to the exacerbation or worsening of troublesome dyskinesia, other problematic dopaminergic symptoms, or other tolerability concerns, a dose reduction from 2 capsules (50 mg LD FPD) to 1 capsule (25 mg LD FPD) per treated episode may be permitted. The medical monitor should be contacted, and the investigator should use his/her clinical judgment to determine whether an additional visit is required and what assessments should be performed (e.g., physical examination, spirometry, etc.). The patient should continue to use 1 capsule (25 mg LD FPD) per treated episode for a period of at least 1 week. If the investigator determines that the tolerability issue has adequately resolved and that the patient has tolerated this dose for at least 1 week, the patient may at that point either resume taking the original dose (2 capsules [50 mg LD FPD] per treated episode) or come into the clinic for an unscheduled visit to receive a reduced-dose study drug kit (35 mg LD FPD). Clinical staff will call the patient 1 to 2 days after the dose escalation to see if the patient has any questions or concerns. If a patient who has escalated back to the full dose (50 mg LD FPD per treated episode) has another tolerability concern that in the opinion of the investigator is of a severity that should necessitate a second reduction in dose, an unscheduled visit will be required and a reduced-dose study drug kit (35 mg LD FPD per treated episode) will be provided. He/she will remain on the reduced dose (35 mg LD FPD) for the remainder of the study; he/she will not be eligible for any additional up-titration in dose.

Safety data will be reviewed by an independent Data Safety Monitoring Board (DSMB) that will include relevant medical experts (including a neurologist and pulmonologist), an independent statistician, and additional representatives (as will be defined in the DSMB Charter). Safety data, including but not limited to AEs, spirometry, vital signs, and ECG data will be reviewed. The safety review will be documented in a DSMB Charter prior to the start of the study. In the event that potential safety issues are identified, the committee may recommend modification of the study design or study termination, which will be communicated promptly with investigators,

Institutional Review Boards (IRBs), Independent Ethics Committees (IECs), and regulatory agencies, in accordance with legal and regulatory requirements.

An overview of the study visit schedule is presented in [Appendix 1](#). Details on the assessments and procedures performed at each visit are presented in [Appendix 2](#) through [Appendix 15](#) and in [Section 10](#).

8. STUDY POPULATION

All patients must meet the inclusion criteria and must not meet any of the exclusion criteria to be eligible for this study. Patients previously enrolled in the CVT-301-002 and CVT-301-003 studies must have completed all of the CVT-301 study visits without any safety issues that would preclude participation in this study according to the investigator. Patients who withdrew from either of the CVT-301 studies prior to completion, *for any reason*, will not be eligible.

8.1. Inclusion Criteria

In order to be eligible to enter the study, patients must meet all of the following criteria:

1. Has signed and dated an IRB/IEC-approved informed consent form before any protocol-specific screening procedures are performed.
2. Is a male or female aged 30 to 85 years, inclusive. Women of child-bearing potential must use protocol-defined contraceptive measures (see [Section 11.1.5](#)) and must have a negative serum human chorionic gonadotropin (hCG) test at screening. These patients must be willing to remain on their current form of contraception for the duration of the study.
3. Patients who have idiopathic PD (i.e., not induced by drugs or other diseases) as defined by fulfilling Steps 1 and 2 of the United Kingdom (UK) Brain Bank criteria, diagnosed after the age of 30 years.
4. Patients who are classified as Stage 1 to 3 (in the ON state) on the modified Hoehn and Yahr scale for staging of PD severity.
5. Patients who have experienced motor fluctuations for a minimum of 2 hours of average daily OFF time per waking day (excluding early morning OFF time) by self-report and confirmed by the PD Diary (on 3 consecutive days) during the screening period.
- 6a. Patients who are on a LD-containing therapy, not including Rytary (or equivalent), must be stable on oral LD-containing therapy for at least 2 weeks prior to SV1 with a LD/DDI-containing regimen
- 6b. Patients who are on a LD-containing therapy, when including Rytary (or equivalent), should be on a stable dose for at least 6 weeks prior to SV1.
- 6c. The frequency of L-dopa administrations must be at least 3 times during the waking day and a total daily LD dose of ≤ 1600 mg.
7. Patients should be stable on other PD medications for at least 4 weeks prior to SV1.

8. Patients must have a $\geq 25\%$ difference between UPDRS Part 3 scores recorded in their ON and OFF states at screening.
9. Patients must have normal cognition as confirmed by a score of ≥ 25 on the Mini Mental State Examination (MMSE), performed in the ON state.
10. 10. Patients must be able to perform a spirometry maneuver in the ON and OFF states, and must have a screening FEV1 $\geq 50\%$ of predicted and an FEV1/FVC ratio $> 60\%$ in the ON state at screening. (A pulmonologist will review the spirometry tracings/morphology of any patient with an FEV1 that is $\geq 50\%$ to $< 60\%$ of predicted or an FEV1/FVC ratio that is $> 60\%$ to $< 70\%$ in order to determine potential eligibility. All CVT-301-naïve patients with an FEV1/FVC ratio that is $> 60\%$ to $< 70\%$ will be required to undergo a bronchodilator challenge and the results must be reviewed prior to entry into the study. Patients with an FEV1/FVC ratio that is $> 60\%$ to $< 70\%$ will complete spirometry before and after the administration of a bronchodilator in a pulmonary function laboratory. Testing will be performed in accordance with the 2005 ATS/European Respiratory Society [ERS] criteria prior to randomization. The results of the bronchodilator challenge will be reviewed by a pulmonologist prior to potential randomization.)

8.2. Exclusion Criteria

Patients meeting any of the following exclusion criteria at screening will not be enrolled in the study:

1. Patients who have dyskinesia of a severity that would significantly interfere with their ability to participate or perform study procedures.
2. Pregnant or lactating females or females wishing to become pregnant.
3. Patients who have any known contraindication to the use of LD, including a history of malignant melanoma or a history of narrow-angle glaucoma.
4. Patients who have had previous surgery for PD (including but not limited to deep brain stimulation [DBS] or cell transplantation).
5. Patients with a history of psychotic symptoms requiring treatment, or suicide ideation or attempt within the prior 12 months (stable regimens [for at least 4 weeks prior to SV1] of anti-depressant and certain low-dose atypical antipsychotic medications are permitted in case they are indicated to treat symptoms other than psychotic symptoms).
6. Patients who have cancer with the exception of the following: basal cell carcinoma or successfully treated squamous cell carcinoma of the skin; cervical carcinoma in situ; prostatic carcinoma in situ; or other malignancies curatively treated and with no evidence of disease recurrence for at least 3 years.
7. Patients taking certain prohibited medications (see [Section 9.4.2](#)).
8. Patients with a history of drug or alcohol abuse within the prior 12 months.
9. Patients with chronic obstructive pulmonary disease (COPD), asthma, or other chronic respiratory disease within the last 5 years.

10. Patients with any contraindication to performing routine spirometry or who are unable to perform a spirometry maneuver (see [Appendix 20](#) for a list of contraindications).
11. Patients with a current history of *symptomatic* orthostatic hypotension despite adequate treatment.
12. Patients with any condition that in the investigator's opinion would make patients unsuitable or interfere with their participation in the study. Potential issues of concern should be raised to the medical monitor during eligibility review.
13. Patients who have any clinically significant abnormality or finding from examination, tests, or history that may compromise patient safety.
14. Patients who have been treated with an investigational drug within 4 weeks or 5 half-lives (whichever is longer) prior to the beginning of the screening period (this includes investigational formulations of marketed products).
15. Prior exposure to CVT-301.

Note: An active or recent (within 3 days) respiratory infection will not disqualify a patient from enrolling in the study. However, all symptoms should be resolved for at least 3 days prior to the baseline visit (TV/OV1) (the screening period may be extended for up to 2 weeks to accommodate this recovery).

8.3. Removal of Patients from Study

A patient may withdraw from the study at any time at his/her own request, or may be withdrawn at any time at the discretion of the investigator for safety, behavioral, or administrative reasons. If a patient is discontinued prematurely at any time after entering the study, the investigator will make every effort to see the patient and complete the TV/OV6 assessments as shown [Appendix 14](#) (for patients in the CVT-301 treatment group) or [Appendix 15](#) (for patients in the observational cohort). If a patient is withdrawn due to an AE, the event must be followed, when possible, until resolution.

An end-of-study page in the electronic case report form (eCRF) should be completed for every patient who receives study drug (if in the CVT-301 treatment group) or enters the TV/OV1 visit (if in the observational cohort), whether or not the patient completes the study. The reason for any early discontinuation should be indicated on this form. The primary reason for a patient withdrawing prematurely should be selected from the following standard categories of early termination:

- *Adverse Event:* Clinical or laboratory events occurred that in the medical judgment of the investigator for the best interest of the patient are grounds for discontinuation. This includes serious and non-serious AEs regardless of relation to study medication.
- *Death:* The patient died.
- *Withdrawal of Consent:* The patient desired to withdraw from further participation in the study in the absence of an investigator-determined medical need to withdraw. If the patient gave a reason for withdrawing, it should be recorded in the eCRF.

- *Protocol Violation*: Significant findings indicating that the study investigator or patient failed to adhere to the protocol requirements (e.g., drug noncompliance, failure to return for defined number of visits). The violation necessitated premature termination of the patient from the study.
- *Lost to Follow-Up*: The patient stopped coming for visits, and study personnel were unable to contact the patient.
- *Other*: The patient was terminated for a reason other than those listed above (to be specified on the eCRF).

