CVT-301-treated patients will be followed in the clinic for the following efficacy measures: serial assessments of UPDRS Part 3 motor score following treatment in the clinic, the occurrence and severity of dyskinesia following treatment in the clinic, the occurrence of ON states during the post-treatment period, the 39-Item Parkinson's Disease Questionnaire (PDQ-39), the Patient Global Impression of Change (PGI-C) rating scale, the Schwab and England (S&E) Activities of Daily Living (ADL) score; UPDRS Part 2 score, and UPDRS Part 4 (Questions 32-35 and 36-39) score. In addition, the total daily ON time without dyskinesia, total daily ON time with troublesome dyskinesia, total daily ON time with non-troublesome dyskinesia, and total daily OFF time will be evaluated in the CVT-301-treated patients based on the PD Diary, which will be completed for the 3 consecutive days prior to SV2, TV/OV1, TV/OV2, TV/OV3, TV/OV4, TV/OV5, and TV/OV6.

All patients, regardless of treatment assignment, will undergo the safety assessments. Patient safety will be evaluated using adverse event (AE) reports, physical examination, vital signs (blood pressure [BP], heart rate [HR], and respiratory rate [RR]), clinical laboratory tests, 12-lead electrocardiograms (ECGs), spirometry, carbon monoxide diffusing capacity (DLco) maneuver, the Parkinson's Disease Impulsive-Compulsive Disorders Questionnaire (QUIP), the Epworth Sleepiness Scale, and the Columbia-Suicide Severity Rating Scale (C-SSRS).

The use of a randomized observational cohort in this study is to permit long-term contemporaneous temporal comparison to CVT-301-treated patients to describe any potential effects of CVT-301 with respect to lung function measurements. These control patients, who are eligible to use any approved treatments to manage their PD motor symptoms, represent a randomized study population that remains naïve to inhalation treatment (to avoid potential confounding interpretation of lung function data) for their PD which is required to ascertain the underlying variability in spirometry and DLco endpoints. Only a limited number of efficacy assessments will be evaluated in the patients randomized to the observational cohort. Selected efficacy measures to assess effects of CVT-301 will be evaluated in the open-label CVT-301-treated patients who use CVT-301 inhalation as a treatment of OFF symptoms.

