10.3.9. Early Withdrawal Visit

Patients in the CVT-301 treatment group who withdraw prematurely will complete the TV6 assessments for the CVT-301 patients (see [Section 10.3.8.1](#)), except for the pre-TV6 DLco assessment, at the time of withdrawal. Patients in the observational cohort who withdraw

prematurely will complete the OV6 assessments for the observational cohort (see [Section 10.3.8.2](#)), except for the pre- OV6 DLco assessment, at the time of withdrawal.

All patients who withdraw early, regardless of treatment group, will be scheduled to undergo a DLco assessment 4 to 5 weeks after completion of the Early Withdrawal Visit. The DLco assessment should be performed in an ON state (as reported by the patient to the pulmonary technician) in the pulmonary function facility. As part of the procedure, a slow vital capacity maneuver will be first, followed by DLco, and then spirometry.

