11.1.11. Other Significant Adverse Events

To ensure patient safety, the investigator should also notify the medical monitor should any AE occur that is considered significant but does not meet criteria for an SAE, or that is considered unexpected. An unexpected AE is an AE that is not identified in nature, intensity, or frequency in the investigational drug brochure. The medical monitor and/or Sponsor may then choose to discontinue the patient from the study. In addition, any field monitor who notes a significant AE

or medical condition while reviewing the eCRFs or source documents at the site must immediately convey this information to the medical monitor.

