12.1. Determination of Sample Size

Approximately 250 CVT-301 treatment patients and 115 control patients will be enrolled in this study. It is assumed that the drop-out rate will be approximately 25%.

Assuming that there is no difference in the changes from baseline between the CVT-301-treated patients and the observational cohort in regards to FEV1, the study has the following power for the comparison between the 2 groups. The upper limit of the 95% confidence interval for the difference between the 2 groups in change from baseline in FEV1 will be less than 0.121 L with 90% power, assuming 188 and 86 patients completing the study in the CVT-301 treatment group and observational cohort, respectively.

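### The protocol has no route for a CVT-301 patient to stop the inhaler and keep scheduled spirometry and DLco to month 12

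*Protocol*

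**What the plan says.** Section 8.3 covers removal from the study. It states "If a patient is discontinued prematurely at any time after entering the study, the investigator will make every effort to see the patient". The assessments of the month-12 visit are to be done at that point. An end-of-study page then records the reason for early termination. Adverse event is one category. Protocol violation is another, with drug noncompliance given as an example.

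Section 10.3.9 applies this to the treated arm: "Patients in the CVT-301 treatment group who withdraw prematurely will complete the TV6 assessments for the CVT-301 patients", except the DLco that normally precedes that visit. One laboratory visit follows 4 to 5 weeks later, with slow vital capacity, DLco and spirometry. The same holds for controls who withdraw.

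Section 11.1.11, on significant or unexpected adverse events, also speaks of the study and not the drug: "The medical monitor and/or Sponsor may then choose to discontinue the patient from the study".

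The schedules for treatment visits 2 to 6 (Appendices 6, 8, 10, 12, 14) each include a supervised dose. The matching observational visits (Appendices 7, 9, 11, 13, 15) have spirometry and no dose.

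On purpose, Section 5.2 says "The use of a randomized observational cohort in this study is to permit long-term contemporaneous temporal comparison to CVT-301-treated patients" in respect of lung function. On size, Section 12.1 says "Approximately 250 CVT-301 treatment patients and 115 control patients will be enrolled in this study" and "It is assumed that the drop-out rate will be approximately 25" percent.

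**The concern.** The primary objective is spirometry over 12 months in CVT-301 patients. The between-group difference and DLco are secondary objectives. Stopping an inhaled drug because of a respiratory effect is informative about exactly these measurements. If stopping means leaving, the values at the remaining scheduled visits are never collected, and no later analysis can recover them.

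The mechanism is one-sided. Both arms lose patients through death, withdrawn consent or loss to follow-up, but only the CVT-301 arm can lose them through stopping an inhaled study drug. The later visits may then compare a treated group from which some affected patients have gone with a control group that has no equivalent filter.

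Two outputs are exposed beyond the mean change. Section 12.5 tabulates 10% and 20% changes seen on two or more consecutive visits, and a patient who leaves after a first decline may have no second scheduled visit. For DLco, the only assessment required after the decision to withdraw comes 4 to 5 weeks later, off drug.

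**Working it through.** **1. Is there any other route?** Setting the sections side by side:

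- 8.3, 10.3.9 and 11.1.11 describe exit from the study only.
- 11.1.5 separates stopping treatment from follow-up, but for pregnancy, and follows only the pregnancy.
- 11.1.8 requires adverse events to be followed after therapy stops, without scheduled spirometry.
- 7 and 10.3 allow dose reduction, so the patient stays in the study but still on drug.

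No sentence says outright that stopping the drug means leaving. That follows from there being no other path.

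**2. What is lost.** A patient who stops just after the month-3 visit has spirometry at withdrawal and again 4 to 5 weeks later. The scheduled values at months 6, 9 and 12 are not collected.

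**3. The plan's own figures (12.1).** Completers = enrolled × (1 − 0.25).

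- CVT-301: 250 × 0.75 = 187.5, stated as 188; loss 250 − 188 = 62.
- Control: 115 × 0.75 = 86.25, stated as 86; loss 115 − 86 = 29.

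This matches "assuming 188 and 86 patients completing the study in the CVT-301 treatment group and observational cohort, respectively".

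**4. Possible shift in the completer mean.** Let p be the share of the CVT-301 arm unseen at month 12, and d the amount by which their FEV1 change is worse than completers'. The full-arm mean is the completer mean minus p × d, so the completer mean is too favourable by p × d. The protocol gives no d; the values below are assumptions.

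| p | d (L) | p × d (L) | share of 0.121 L |
|---|---|---|---|
| 0.25 | 0.10 | 0.025 | 21% |
| 0.25 | 0.20 | 0.050 | 41% |
| 0.15 | 0.10 | 0.015 | 12% |
| 0.15 | 0.20 | 0.030 | 25% |

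For the group difference the shift is p × d in the CVT-301 arm minus p × d in controls. With 25% lost and the same d in both arms it is zero.

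**5. Effect on the precision statement.** Section 12.1 says the upper 95% limit "will be less than 0.121 L with 90% power" if there is no true difference. No SD is given, so it is back-solved, taking the interval as two-sided:

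- SE = 0.121 / (1.960 + 1.282) = 0.0373 L.
- SD = 0.0373 / √(1/188 + 1/86) = 0.287 L.

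If the true difference were 0.121 L, the chance that the upper limit still falls below 0.121 L is Φ(shift/SE − 1.960):

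- no shift: 2.5%
- shift 0.025 L: 9.8%
- shift 0.050 L: 26.7%

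Section 12.1 does not call 0.121 L a margin; it serves here only as a yardstick.

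**The case against.** **Much is already collected.** Leavers have spirometry at withdrawal and 4 to 5 weeks later, so a falling FEV1 that prompts withdrawal is measured if the patient attends. Anyone with one dose is in the safety population. The single-visit threshold tables can catch the decline, and the mixed model uses all visits before withdrawal. A reader might infer that patients vanish from the dataset when an effect appears; the protocol does not support that. What stands is narrower: there are no scheduled values after the laboratory visit, and the model must assume missingness at random.

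**Patients with tolerability problems can stay.** Dose reduction is allowed, home use is as needed with no stated minimum, and noncompliance is listed only where it made termination necessary. So it would also be wrong to infer that only patients who tolerate the inhaler are kept. None of this helps a patient who stops altogether.

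**Background therapy is not the contrast.** A reader might infer that controls alone can change PD treatment and remain in follow-up. Sections 7 and 10.3 allow changes in both arms. Section 9.4.2 also requires dopamine agonists, COMT inhibitors and MAO-B inhibitors to stay stable throughout, which must be reconciled with the general permission to modify. The arms differ in having a study drug to stop.

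**On-drug values suit a safety question.** Adding off-drug months could dilute a reversible effect and hide harm. This stands and shapes the fix.

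**Analysis choices belong in the SAP.** Section 12.6 foresees missing-data sensitivity analyses, though under exploratory efficacy, and the SAP may extend them to spirometry. It cannot supply measurements that were not taken.

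**Conclusion.** The gap is real and should be closed: a CVT-301 patient who stops the inhaler has no stated way to continue scheduled spirometry and DLco to month 12. It bears on the 12-month characterization in the treated arm, the secondary between-group difference, and the consecutive-visit tabulation.

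The size is unknown. The 0.025 to 0.05 L is a ceiling under stated assumptions: every CVT-301 leaver, whatever the reason, is 0.10 to 0.20 L worse; controls have no selection; and the estimate rests on completers alone. The mixed model and the withdrawal spirometry would recover part, and similar selection in controls would offset it. The figures show that the loss could matter against 0.121 L, not that it does.

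**What to change.** In Sections 8.3 and 10.3.9, separate stopping CVT-301 from withdrawing from the study.

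- Patients who stop the drug for any reason and still consent continue on the observational schedule (Appendices 7, 9, 11, 13, 15), with spirometry and DLco to month 12 and no dosing.
- Record the last-dose date and the reason for stopping the drug separately from the end-of-study page.
- Do not list drug noncompliance alone as an example of grounds for leaving the study.
- Align Section 11.1.11 so that it says whether the patient is discontinued from drug or from study.
- Report the between-group spirometry difference on all scheduled values and on on-drug values, with neither replacing the other.

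This sets no rule on when the drug should be stopped. It costs a protocol amendment, a treatment-stop eCRF record, and clinic and DLco visits for stoppers that were already planned at enrolment. Patients who die, withdraw consent or are lost remain unseen, so only part of the 25% can be recovered.
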